8.2 Overview of Safety Analysis Methods

Safety data will be analyzed descriptively using the safety population described in Section 4.2. Unless specified, all safety summaries will be presented by descriptive statistics, such as number of subjects (n) and percentage for categorical variables and number of subjects (n), mean, standard deviation, median, minimum, and maximum for continuous variables.

8.3 Extent of Exposure

The length of exposure (in days) of study medication will be calculated based on the dates of first and last dosing of study medication (last dosing date - first dosing date + 1). Length of exposure will be summarized by dose (4 mg/day and 6 mg/day) and treatment group on the safety population as continuous values.

For subjects lost to follow-up, no imputation of the length of exposure will be conducted. For subjects who discontinue the study early but return for a follow-up visit, the follow-up data will be used to impute the length of exposure.

8.4 Adverse Events

All AEs will be coded using MedDRA Version 19.0. An AE is any untoward medical occurrence:

- that occurred before, on or after the first dose of study medication,
- with a missing start date and a stop date before, on or after the first dose of study medication, or
- with both a missing start and stop date.

Untoward medical occurrences that occur between the time of informed consent/assent and first study drug administration are pre-treatment events. Those that occur after first administration of study drug are considered AEs. Clinically significant abnormal objective findings (eg, clinical laboratory value, ECG value, and physical examination observation) will also be recorded as AEs.

A serious adverse event (SAE) is an AE that meets one or more of the following criteria:

- Results in death.
- Is life threatening.
- Requires hospitalization or prolongation of existing hospitalization.
- Results in persistent or significant disability or incapacity.
- Is a congenital anomaly or birth defect.
- Is an important medical event that may jeopardize the subject or may require a medical or surgical intervention to prevent one of the outcomes listed

above. Examples of such medical events include allergic bronchospasm requiring intensive treatment in an emergency room or at home, blood dyscrasias or convulsions that do not result in inpatient hospitalization.

An AE is considered treatment emergent if it started during or after administration of the first dose of study medication. In addition, medical history events that worsen in severity after the start of dosing will be considered treatment-emergent adverse events (TEAEs). If a subject discontinues early from the study and has an AE after his/her last dosing date, the AE will be deemed as treatment emergent if it occurs ≤ 72 hours after the last dose and not as treatment emergent if it occurs >72 hours after the last dose of study medication. AEs with partial start dates will be imputed as outlined in Section 8.1 and assigned to the associated treatment period.

Summary Tabulations

An overview of the frequency, i.e., the number and percentage of subjects and events with at least one of the following AEs, will be presented by treatment group (placebo, dasotraline 4 mg/day, dasotraline 6 mg/day, and combined dasotraline [4 mg/day + 6 mg/day]):

- All TEAEs
- SAEs
- TEAEs leading to discontinuation
- Severe TEAEs
- TEAEs related to study medication
- Severe TEAEs
- SAEs related to study medication
- AEs leading to death

System Organ Class and Preferred Term Tabulations

The frequency of subjects reporting TEAEs, along with the frequency of events, will be summarized within each system organ class (SOC) and preferred term (PT) by treatment group. The SOC terms and PTs will be presented in decreasing order of the total number of subjects in the combined dasotraline group (4 mg/day and 6 mg/day)

(frequency) who experienced each AE. System organ class terms and PTs with the same frequency will be presented alphabetically.

Each subject will be counted only once within each SOC and within each PT. If a single subject experienced the same AE more than once within a treatment period, the subject will be counted once per SOC and PT for that AE. For subjects that experienced AEs with multiple severities, the AE with the highest known severity within each SOC and PT will be counted. Adverse events with unassigned/unknown severity will be categorized as severe.

For summaries by relationship to the study medication, AEs will be grouped as “related” or “not related.” AEs assessed as “possible,” “probable,” or “definite,” will be grouped as “related.” If a subject reports more than one AE within the same treatment regimen, SOC and PT, and any are related, it will be summarized as related. AEs whose relationship to treatment is assessed as “not related” or “unlikely” will be grouped as “not related.” Events with unassigned/unknown relationship to study medication will be considered related to study medication.

The frequency of subjects reporting the following AEs, along with the frequency of events, will be summarized and presented by treatment group and MedDRA SOC and PT for the Safety population:

- All TEAEs (including number of events and subject incidence)
- SAEs
- Non-SAEs
- TEAEs leading to discontinuation
- TEAEs by maximum severity (mild, moderate, severe)
- TEAEs by relationship to the study treatment (related, or not related)
- SAEs by relationship to the study treatment
- AEs leading to death

By-Subject Listings

By-subject listings including relevant information (i.e. treatment, age, sex, race, duration of AE, severity, relationship, outcome, action taken, etc.) will be presented for:

- All AEs
- SAEs
- AEs leading to death
- AEs leading to discontinuation (per the case report form)

The onset of AEs will be calculated relative to the first dose of study medication. The duration of AEs in days will be calculated as the difference between the onset and resolution dates of the AE. If the AE is ongoing at the end of the study, or the resolution date is unknown, the duration will be presented as 'Unknown'.

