12. SAFETY REPORTING

12.1. Definitions

12.1.1. Adverse Events

An adverse event (AE) is any untoward medical occurrence associated with the use of a drug in humans, whether or not considered drug related.

Untoward medical occurrences that occur between the time of informed consent/assent and first study drug administration are pre-treatment events. Those that occur after first administration of study drug are considered AEs.

An AE can, therefore, be any unfavorable and unintended sign (including an abnormal laboratory finding), symptom, or disease occurring after the administration of a medicinal (investigational) product, whether or not considered related to the medicinal (investigational) product. AEs may include the onset of new illness and the exacerbation of pre-existing conditions. AEs will be collected from after first administration of study drug to the last study visit.

Lack of efficacy may be an expected potential outcome and should not be reported as an AE unless the event is unusual in some way.

New signs and symptoms of underlying disease, or signs and symptoms of emerging disease must be recorded as AEs.

The Investigator should attempt to establish a diagnosis of the event based on signs, symptoms, and/or other clinical information. In such cases, the diagnosis should be documented as the AE and not the individual signs/symptoms.

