12.3. Collection and Recording of Adverse Events

All pre-treatment events and AEs must be recorded in the subject's study records/source documents in accordance with the Investigator's normal clinical practice. All pre-treatment events and AEs/all AEs must be recorded on the CRF.

All AEs will be followed until resolution, stabilization of the condition, the event is otherwise explained, or the subject is lost to follow-up.

Each AE is to be evaluated for duration, severity, frequency, seriousness, action taken with the study treatment, outcome, and causal relationship to the study treatment. Definitions for severity, frequency, action taken with the study treatment, outcome, and causal relationship to the study treatment are presented below.

The severity of AE:

- **Mild** - Ordinarily transient symptoms that do not influence performance of subject's daily activities. Other treatment is not ordinarily indicated.
- **Moderate** - Marked symptoms sufficient to make the subject uncomfortable. Moderate influence on performance of subject's daily activities. Other treatment may be necessary.
- **Severe** - Symptoms cause considerable discomfort. Substantial influence on subject's daily activities. May be unable to continue the study, and other treatment may be necessary.

The frequency of AE:

- **Once** – an isolated episode.
- **Intermittent** – occurs on two or more separate occasions.
- **Continuous** – does not abate from date of onset to date of resolution.

The action taken with the study treatment:

- **Drug Interrupted** – Study drug stopped temporarily.
- **Drug Withdrawn** – Study drug stopped permanently.
- **Dose Not Changed**
- **Not Applicable**.
- **Unknown**

The outcome of the AE:

- **Recovered/Resolved**
- **Recovering/Resolving**
- **Not Recovered/Not Resolved**
- **Recovered/Resolved with Sequelae**
- **Fatal**

- **Unknown**

The causal relationship of the AE to the study treatment:

- **Not related**

- **Not related** - Improbable temporal relationship and is plausibly related to other drugs or underlying disease.
- **Unlikely** - occurred within a reasonable time frame after administration/discontinuation of the study drug, but there is a likely association of an intercurrent/underlying medical condition or other drugs.

- **Related**

- **Possible** - occurred in a reasonable time after study drug administration, but could be related to concurrent drugs or underlying disease.

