15.3.6.1. Adverse Events

All AEs will be coded using Medical Dictionary for Regulatory Activities (MedDRA) version 18.0 or higher. AEs are untoward medical occurrences:

- that occurred on or after the first dose of study medication,
- with a missing start date and a stop date on or after the first dose of study medication, or
- with both a missing start and stop date.

AEs will be summarized by treatment and by MedDRA system organ class (SOC) and Preferred Term (PT).

The following AEs will be summarized and presented by treatment group and by MedDRA SOC and PT for the Safety population:

- All AEs (including number of events and subject incidence).
- Serious AEs.
- AEs leading to discontinuation.
- AEs by maximum severity (mild, moderate, severe).
- AEs by relationship to the study treatment (related, or not related).
- Serious AEs by relationship to the study treatment.
- AEs leading to death.

The following conventions will be followed in summarizing AEs:

- For subject incidence summaries, each subject will be counted only once within each SOC and within each preferred term.

- If a subject reports more than one AE within a preferred term and/or a body system, the AE with the highest known severity within each body system and within each preferred term will be included in the summaries by severity.
- For summaries by relationship to the study medication, AEs will be grouped as “related” or “not related.” AEs assessed as “possible,” “probable,” or “definite,” will be grouped as “related.” If a subject reports more than one AE within the same treatment regimen, SOC and PT, and any are related, it will be summarized as related. AEs whose relationship to treatment is assessed as “not related” or “unlikely” will be grouped as “not related.”

A listing of AEs, as well as a listing of deaths, SAEs, or AEs leading to discontinuation, will be presented.

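### SAP 8.4 defines adverse events to include those before the first dose, against Protocol 15.3.6.1 and its own next paragraph, so pre-treatment events can enter summaries that have no treatment-emergent limit

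*SAP*

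**What the plan says.** SAP 8.4 opens with three bullets that define an AE. The first covers an occurrence "that occurred before, on or after the first dose of study medication". The second covers one "with a missing start date and a stop date before, on or after the first dose of study medication, or"; the third covers an event with neither date. The paragraph directly below says something different: "Untoward medical occurrences that occur between the time of informed consent/assent and first study drug administration are pre-treatment events", and "Those that occur after first administration of study drug are considered AEs".

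Protocol 15.3.6.1 has the same three bullets without the pre-dose period. Its first reads "that occurred on or after the first dose of study medication" and its second "with a missing start date and a stop date on or after the first dose of study medication, or". Protocol 12.1.1 agrees: "AEs will be collected from after first administration of study drug to the last study visit". Protocol 11.4.1 also treats earlier occurrences as pre-treatment events. These events are nevertheless in the data, since Protocol 12.3 states "All pre-treatment events and AEs/all AEs must be recorded on the CRF". SAP 12.2 declares no change from the protocol's planned analysis.

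Within SAP 8.4, the all-event, discontinuation, severity and all-event relationship tables are restricted to TEAEs. The tables of SAEs, SAEs related to study medication, SAEs by relationship, non-SAEs and AEs leading to death are not. Nor are the AEs of special concern in SAP 8.5 or the safety summaries and ROC outcome in SAP Section 10.

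**The concern.** The bullets are the operational part of the definition. They carry the missing-date handling, and they track the protocol's bullets except for the added pre-dose period. One programmer who builds the AE flag from the bullets and another who builds it from the next paragraph would produce different tables from the same data.

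What is at stake is attribution. An event that began and ended before any study drug was taken could be counted in a treatment column. Two features of the plan could make this worse:

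- SAP 8.4 counts an unknown relationship as related. Protocol 12.3 requires a causality assessment for each AE but does not say so for pre-treatment events. A pre-dose event without that assessment, if it reached the table of SAEs by relationship, would appear as drug-related.
- In SAP Section 10, AEs of special concern are the outcome of a logistic regression on mg/kg. A pre-dose event would then be modelled as a function of a dose not yet taken.

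**Working it through.** The plan gives no figure to reproduce. The check takes six event-date patterns through each rule.

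**Rules.** (a) Protocol 15.3.6.1 bullets. (b) SAP 8.4 bullets. (c) SAP 8.4 next paragraph. (d) SAP 8.4 TEAE rule, meaning onset during or after the first dose, after the SAP 8.1 imputation that sets a completely missing start date to the first-dose date. Pattern 2 assumes no worsening after dosing, because SAP 8.4 makes medical history that worsens a TEAE.

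| Pattern | (a) Protocol AE | (b) SAP bullets AE | (c) SAP next paragraph AE | (d) TEAE |
|---|---|---|---|---|
| 1. Start and stop before first dose | No | Yes | No | No |
| 2. Start before, stop after first dose | No | Yes | No | No |
| 3. Start missing, stop before first dose | No | Yes | No | **Yes** |
| 4. Start missing, stop after first dose | Yes | Yes | Not settled | Yes |
| 5. Both dates missing | Yes | Yes | Not settled | Yes |
| 6. Start after first dose | Yes | Yes | Yes | Yes |

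**Result.** Rules (a) and (b) differ on patterns 1, 2 and 3. Patterns 1 and 2 can reach only the summaries without a TEAE limit. Pattern 3 can also reach the TEAE tables, because SAP 8.1 imputes the start date without looking at the stop date. The record would then have a start later than its stop.

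**Which summaries are open.** The safety population (SAP 4.2) requires at least one dose. That restricts subjects, not event dates, and the analysis is by treatment received.

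- *Non-SAEs*: no TEAE limit, and no seriousness flag is needed to qualify. This is the main exposure.
- *AEs of special concern (8.5), and the mg/kg summaries and ROC analysis (Section 10)*: no TEAE limit stated.
- *SAEs*: no TEAE limit, but Protocol 12.4.1 requires SAE reporting only after first administration, so few pre-dose events may carry a seriousness assessment. Exposure is smaller.
- *AEs leading to death*: the subject must have been dosed, so only a fatal event with onset before dosing could enter. Exposure is slight.

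**Why a TEAE limit is not the remedy.** For subjects who discontinue early, SAP 8.4 does not count an event more than 72 hours after the last dose as treatment-emergent. Protocol 15.3.6.1 has no such end cut. Restricting the SAE and death tables to TEAEs would remove events that the protocol keeps.

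**The case against.** The strongest defence is that SAP 8.4 already contains the right rule. Its next paragraph separates pre-treatment events from AEs, and the SAE definition that follows starts from an AE. On that reading the SAE, non-SAE and death tables exclude pre-dose events. A wide definition with TEAEs as a subset is also a usable convention for listings, and SAP 8.4 does list all AEs. The table and listing specifications are separate documents (SAP Section 1) and may settle the filter. This defence stands to the extent that pre-dose events *can* enter, not that they *will*. It does not reconcile two adjacent statements, explain the undeclared departure from the protocol, or deal with pattern 3.

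A reader might infer more than the documents support:

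- *That most of the observation time in these tables precedes treatment.* First dose (Day 1) to the end-of-study visit (Day 21 ± 2) is 18 to 22 days. Screening of 35 days would give 35/(35+22) = 61% to 35/(35+18) = 66%. But Visit 1 may be as late as Day -8, which gives 8/(8+22) = 27% to 8/(8+18) = 31%. These are shares of time, not of events, and no event count is given.
- *That methylphenidate withdrawal makes such events numerous.* The washout begins 3 to 5 days before Day -1, so only about 4 to 6 days before Day 1. It does not span the screening period.
- *That the drug-placebo contrast is diluted.* Events before randomization are expected to be balanced between randomized arms, safety is analysed descriptively (SAP 8.2), and the number of events is unknown. No claim about the size of an effect on the contrast can be supported.

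**Conclusion.** The definition in SAP 8.4 is wrong as written. It contradicts Protocol 15.3.6.1 and its own next paragraph, and SAP 12.2 does not declare the difference. Read literally, it admits three date patterns that the protocol excludes, and one of them also reaches the TEAE tables through SAP 8.1.

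The severity is minor. Apart from that one pattern, the principal AE tables are protected by the TEAE limit, and no efficacy conclusion depends on the affected tables. The conclusion assumes that the bullets, rather than the next paragraph, drive the programming, and that the separate table specifications do not already impose a first-dose cut. The number of affected events cannot be derived from the documents and may be zero.

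**What to change.** 1. In SAP 8.4, restore the protocol's limit of on or after the first dose in both bullets, so that they match Protocol 15.3.6.1 and the SAP's next paragraph.
2. Apply that first-dose cut, not a TEAE limit, to the SAE, non-SAE, death and special-concern summaries. Carry it through to the mg/kg summaries and the ROC outcome in Section 10.
3. In SAP 8.1, check the stop date before imputing a start date. An event that stopped before the first dose stays a pre-treatment event.
4. List pre-treatment events separately.

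The cost is a few words in the SAP, one first-dose flag and one date check in the programs, and one extra listing. No data collection changes. If the sponsor wants the wide definition for listings, it should be confined to them and declared in SAP 12.2.

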11.4.4. Physical and Neurological Examinations

Clinically significant physical examination findings, as judged by the investigator, at screening will be recorded as medical history and after screening will be recorded as AEs or pre-treatment events depending on the timing in relationship to the first dose of study drug.

Neurological examination parameters will be assessed by the investigator as normal or abnormal.

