8.7 Physical and Neurological Examinations

A full physical examination will be performed at Screening (Visit 1) and at the EOS (Visit 6). Body weight will also be measured at Screening (Visit 1), Visit 4, Visit 5, and at the EOS (Visit 6). Height will be measured at Screening (Visit 1).

Clinically significant physical examination findings, as judged by the investigator, at screening will be recorded as medical history and after screening will be recorded as AEs or pre-treatment events depending on the timing in relationship to the first dose of study drug. Abnormal physical exam results will appear in medical history and/or AEs displays and will not be displayed separately.

Neurological examinations will be performed at Screening (Visit 1) and at the EOS (Visit 6) and the parameters will be assessed by the investigator as normal or abnormal. Neurological examination assessments will be summarized using summary statistics for categorical variables (normal/abnormal) by visit. A shift table for baseline condition versus the worst result during the course of the study period (Abnormal > Normal) will be presented by treatment.

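### The treatment-emergent rule for worsening names only medical history events, so a pre-treatment event that worsens on study drug may be missed, depending on how the site records it

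*SAP*

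**What the plan says.** SAP 8.4 sets out two routes to TEAE status. The first is by start date: "An AE is considered treatment emergent if it started during or after administration of the first dose of study medication". The second is by worsening: "medical history events that worsen in severity after the start of dosing will be considered treatment-emergent adverse events".

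The same section defines a further class: "Untoward medical occurrences that occur between the time of informed consent/assent and first study drug administration are pre-treatment events". Both documents keep this class apart from medical history. For physical examination findings, SAP 8.7 says that those made "at screening will be recorded as medical history and after screening will be recorded as AEs or pre-treatment events", and Protocol 11.4.4 uses the same split, with later findings classed by their timing relative to the first dose.

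Protocol 12.1.1 says that "AEs may include the onset of new illness and the exacerbation of pre-existing conditions". On recording, Protocol 12.3 says only that "All pre-treatment events and AEs/all AEs must be recorded on the CRF". Neither document says whether a pre-treatment event that worsens after the first dose becomes a new record or a change to the existing one.

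**The concern.** The SAP accepts that worsening on study drug should count, but grants this only to conditions held as medical history. It gives no reason why a complaint already in the history should count when it worsens while one that began during screening should not.

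Timing gives the point some weight in this trial. Every child stops methylphenidate 3 to 5 days before Day -1 and takes the first dose on the evening of Day 1 (Protocol 7.1 and 10.3.1), so there is a short off-treatment period just before dosing in which new complaints could arise. The common adverse events in the adult dasotraline study included insomnia, decreased appetite and headache (Protocol 4.3). If a complaint of this kind were present at first dose and the drug made it worse, an omission would fall mainly in the dasotraline arms and would understate the difference from placebo.

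**Working it through.** The plan has no figure to reproduce. The check is a reading of the rule case by case, followed by a rough size on assumed rates.

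**Step 1. Apply the two routes.** Take a mild complaint that becomes severe on Day 4 of study drug.

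| Case | Start-date route | Worsening route | TEAE? |
|---|---|---|---|
| (a) Began Day -3 as a pre-treatment event; severity raised on the same record | Not met: start is before first dose | Not met: not medical history | No |
| (b) Began Day -3 as a pre-treatment event; worsening entered as a new AE with Day 4 onset | Met | Not needed | Yes |
| (c) Found at screening and held as medical history; worsens on Day 4 | Not met | Met | Yes |

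Cases (a) and (b) are the same clinical course with different counts. The omission arises only in (a).

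**Step 2. Look for a rule elsewhere that captures case (a).** Protocol 15.3.6.1 defines AEs by timing relative to the first dose and has no worsening rule. SAP 8.1 imputes missing start dates only. It also produces an odd contrast: an event with only month and year known, in the month of first dose, is moved to the first-dose date and becomes a TEAE, while the same event with a complete pre-dose date does not.

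**Step 3. Identify the outputs affected.** In SAP 8.4 these are the TEAE tables: all TEAEs, by severity (including severe), by relationship, and leading to discontinuation. The SAE, death and non-SAE tables and the listing of all AEs are not restricted to TEAEs, nor is the summary of AEs of special concern in SAP 8.5.

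**Step 4. Rough size.** The documents give no rates. Let p be the share of children with a pre-treatment event still present at first dose, assumed 5% to 20%, and w the share of those who worsen on drug, assumed 10% to 30%. The arm sizes, 55 planned and about 20 at 6 mg/day, are from SAP 2.4.

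Children at risk of omission = N × p × w

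| | Low (5%, 10%) | Central (10%, 20%) | High (20%, 30%) |
|---|---|---|---|
| N = 55 | 55 × 0.05 × 0.10 = 0.3 | 55 × 0.10 × 0.20 = 1.1 | 55 × 0.20 × 0.30 = 3.3 |
| N = 20 | 20 × 0.05 × 0.10 = 0.1 | 20 × 0.10 × 0.20 = 0.4 | 20 × 0.20 × 0.30 = 1.2 |

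The number actually lost is this figure times the share u of such worsenings that are entered on the old record. With u = 0.5, also an assumption, the central case for 55 children is 1.1 × 0.5 = 0.55.

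**The case against.** The strongest answer is that the protocol already offers a route that works. It divides occurrences at the first dose and allows the exacerbation of a pre-existing condition to be an AE. At first dose, a complaint that began on Day -3 is pre-existing, so its later worsening can be entered as an AE with a post-dose onset and qualifies by start date. The causality categories in Protocol 12.3 point the same way: possible, probable and definite each require occurrence within a reasonable time after study drug administration, which a pre-dose start date does not fit. Nothing tells sites to raise the severity on the old record. This stands, and it rules out the reading that a worsened pre-treatment event is never treatment-emergent.

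It does not close the gap. Protocol 12.1.1 is permissive, and no instruction to open a new record is given either. If the start-date route were relied on to capture every exacerbation, the SAP would not need its separate sentence for medical history.

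A second answer is that the event would still be visible, because the SAP's AE definition takes in anything "that occurred before, on or after the first dose of study medication" and the non-SAE table and AE listing are not limited to TEAEs. This holds only in part. The paragraph after that definition puts events before first dose in a class of their own, and the non-SAE table would not show that the event had worsened on drug.

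A reader might also infer that one to three children are lost from each arm, or that washout produces insomnia, appetite loss or headache. The documents support neither. The rates are assumed, they give at most 1.2 children in an arm of 20, and they reach 3.3 in an arm of 55 only with both rates at their upper limits and every worsening entered on the old record. The adverse events in Protocol 4.3 come from treated adults, and the only change the documents describe in washout is worsening of ADHD symptoms.

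**Conclusion.** The gap in the wording is real, and its effect is conditional. A pre-treatment event that worsens after the first dose may be missing from the TEAE tables when the worsening is entered on its original record, and is counted when it is entered as a new AE. TEAE status then depends on site habit, which the SAP should settle.

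The size cannot be established from the documents and is probably small: about one child or fewer per arm of 55 under the central assumptions, before allowing for the share of worsenings entered on the old record. Any bias against detecting harm rests on the further assumption that dasotraline causes the worsening. Safety is summarised descriptively (SAP 8.2) and the efficacy analyses are not touched. The point is worth correcting because the remedy is cheap and removes a possible understatement of worsening on drug.

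**What to change.** In the SAP 8.4 sentence on worsening, add 'and pre-treatment events' after 'medical history events', and end it with 'with onset at the date of worsening'. The onset date is also needed to apply the 72-hour limit in the same section for children who stop early. State in the SAP and in the instructions to sites that such a worsening is recorded as a new AE. While the section is open, reconcile the AE definition that includes events before first dose with the paragraph that calls them pre-treatment events.

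The cost is a few words and a note to sites. TEAE counts may rise slightly. The rule also needs a severity grade from before the first dose: Protocol 12.3 asks for severity of each AE and does not say whether pre-treatment events are graded, so this should be confirmed. Where a site has already changed a severity without dating the change, a query will be needed to fix the onset.
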